- Naloxone (opioid antidote) was administered approximately once a day in Seattle by medics attending to opioid overdoses in 2011. Almost all are transported to the HMC ED.
- On August 22, 2012 the Director of the Office of National Drug Control Policy, Gil Kerlikowske, called for increased action to prevent drug overdose deaths, including wider distribution of naloxone.

Objectives

Primary Aims

The primary aims are to test whether those who receive the intervention compared to standard care have:

[figure not shown]
- 1) Lower rates of opioid non-fatal and fatal overdose
- 2) Reduce drug use, in appropriate medication use, and other overdose risk behaviors

Secondary Aims

The secondary aims are to test whether those who receive the intervention compared to standard care have:

- 3) More appropriate health care utilization (e.g. fewer emergency department visits and admissions to inpatient care)
- 4) Lower total health care costs
- 5) Determine the prevalence of HIV risk behaviors among heroin and pharmaceutical opioid users at risk for overdose and whether the intervention impacts these behaviors.

Study Design

This prospective, multi-site, randomized clinical trial will compare standard care to a novel intervention that combines OOPEN with BBCC for heroin users (n=500) and pharmaceutical opioid users at elevated risk for overdose (n=500). The study will take place at Harborview Medical Center (HMC) , University of Washington Medical Center (UWMC), and Evergreen Treatment Services. The primary outcomes are subsequent opioid overdoses, ascertained by self-report interviews at 3, 6 and 12 months after recruitment as well as via administrative records for at least 24 months and self-reported drug use and other overdose risk behaviors. Secondary outcomes include: health care utilization, direct health care costs and impact on HIV risk behaviors.

Eligibility Criteria

Inclusion for all subjects:

- 1) Meets study definition of elevated risk of future opioid overdose
 - Reason for visit is opioid overdose (regardless of frequency of use), or
 - Use of pharmaceutical opioids not prescribed to the patient 2 or more times in the prior month, or
 - Use of other opioids, alcohol, benzodiazepines or stimulants within two hours of using opioids 2 or more times in the prior month, or
 - Average daily dose of prescribed opioids consumed is greater than 10 mg morphine equivalent analgesic dose or higher for 15 or more days in the last 30.

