Secondary data on health care and drug treatment utilization will be obtained from Washington State (separate IRB action pending) using the following sources:

- Treatment and Assessment Report Generation Tool (*TARGET*) for drug treatment admissions data
- The Comprehensive Hospital Abstract Reporting System (CHARS) for hospital admissions

Information on any ambulance transports will be obtained from the Seattle Fire Department's Medic 1 unit.

In the event of a subject death during the study we will request information on cause of death from the King County Medical Examiner's Office. If a subject cannot be located we will also check this source to see if they have died and if so to obtain data on the cause of death. If we are unable to locate a subject during the course of the study or at final follow-up we will utilize the King County Jail Inmate Look-up Service. At no time will subjects be contacted or study procedures attempted while the subject is incarcerated.

Intervention Description

Standard care for patients who have used opioids would vary according to individual clinical need and might include referral to drug treatment or detoxification services. Standard care would not include OOPEN and BBCC interventions as specified in this grant. After baseline data are obtained subjects assigned to the intervention undergo the following procedures:

A brief behavior change counseling (BBCC) session

- Conveys subjects' risk for overdose, based on the baseline measures
- Engages them in a reflective discussion of the pros and cons of their current patterns of use
- Has the patients identify behavior change(s) they are interested in making to improve their health
- Encourages them to share opioid overdose prevention and intervention information and materials with their family, friends, housemates, and/or drug using partners.

Education and training on opioid overdose prevention and intervention with naloxone (OOPEN)

- Subjects will view a training video on study laptops that reviews:
 - Information on risk factors for overdose and how to prevent and reduce the risk of overdose

- How to recognize an opioid overdose
- The importance of calling 911
- How to intervene in an overdose
 - Positioning a victim in rescue position
 - Brief overview of rescue breathing
 - Training on how and when to administer naloxone

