- Subjects will be given a study brochure that covers the information in the video and reviews the Washington State 911 Good Samaritan overdose law which provides immunity from prosecution for drug possession charges to overdose victims and bystanders who seek aid in an overdose event.
- Prescribing and dispensing overdose rescue kits including 2 doses of intra-nasal naloxone, a disposable rescue breathing mask, and disposable gloves.
- Subjects in the intervention group will be informed that they may have one replacement of the naloxone kit (2 doses) during the 12 month study period.

We expect the intervention to take 30-45 minutes on average based on our experience and that this is feasible and reasonable for subjects and interventionists.

Fidelity assessment for the BBCC will be done with the shortened Motivational Interviewing Treatment Integrity (MITI) instrument.

Schedule of and Sources Data Obtainment

MEASURES	DATA SOURCES AND TIMING					
	Interview			Administrative		
	Case Report Form	Base-line	3 & 6 mos.	12 mo.	Up to 10 yrs.	Up to 10 yrs.
PRIMARY AIMS						
Aim 1: Overdose						
Subject overdosed prior 3/6* months	X		X			
Subject overdosed Y/N & Date						X
Aim 2: Drug use and other overdose risk behaviors						
Alcohol/Drugs 3/6 month use frequency	X		X		X	
Opioid use following interruption past 3/6 months	X		X		X	
Using opioids without others present	X		X		X	
Avg. daily opioid dose- Prescribed Opioid Users	X		X		X	
Opioid substitution drug treatment prior 3/6	X		X		X	
Other drug treatment sought or used prior 3/6	X		X		X	
SECONDARY AIMS						
Aim 3: Health care utilization						

ED, Outpatient, Inpatient and Ambulance- # & Aim 4: Health care costs Hospital-based total direct health care costs			x	x
Aim 5: HIV Risk Behaviors	x	x	x	x
CO-VARIATES & POTENTIAL EFFECT MODIFIERS				
Demographics	x			
Employment, health insurance, income, housing	x	x	x	
Alcohol/Drugs ages of first use	x			
Medical status and satisfaction (WHO QOL BREF, EQ-5D- 3L)	x	x	x	
Behavior change plans and readiness	x			
Overdose lifetime history	x			
Possessed, "carried" naloxone, # of days past 3/6	x	x	x	
Overdose # witnessed events past 3/6 months	x	x	x	
Source of naloxone- Study, other	x	x	x	
Subject had naloxone administered to them, #, by Disposition of naloxone	x	x	x	x
Subject had negative/allergic reaction to naloxone	x	x	x	
FIDELITY ASSESSMENT OF BASELINE				
Overdose prevention & intervention training. Item Motivational Interviewing Treatment Integrity 3.1.1	x			

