*Past 3 months timeline for 3 and 6 month follow ups, past 6 months used at 12 month follow up.

Brief Behavioral Change Counseling (BBCC)

The BBCC will be conducted according to the demeanor and guidelines of Motivational Interviewing (MI), a style for counseling patients about sensitive behaviors and for giving them information to enhance their health and safety in a non-judgmental manner. MI has been widely implemented in brief intervention studies for drug use and other behavior change. MI is non-confrontational and respectful of subjects' autonomy to discuss or not discuss sensitive topics. The BBCC will consist of 4 elements:

- 1) The interventionist will show to the patient an approximately 8-minute video on overdose prevention, recognition and intervention, which subjects will view on a laptop while they are using headphones. The interventionist will debrief the video with subjects and answer questions.
- 2) Next, the interventionist will review with subjects their overdose risk. This task involves informing subjects of the “good news” about overdose risks they are NOT incurring in their current behaviors for the purpose of reinforcing and hopefully continuing more positive health behaviors (e.g., not inappropriately mixing other drugs or alcohol with

opiates). Next, the interventionist will respectfully and in a neutral tone review with subjects the behaviors that currently place them at risk for opiate overdose (e.g., using opiates when alone or after a long period of abstinence).

- 3) From the video and risk feedback, the interventionist will segue into an open discussion of any changes subjects are thinking of making to increase their safety from overdosing. If at any time during the interview, subjects indicate that they would prefer to quit opiates or to seek opiate detox or treatment, the interventionist will help with these referrals. The discussion will culminate in a summary of healthy changes, if any, that subjects intend to make. Subjects will take with them a handout that has been customized to summarize any changes subjects indicate that they want to make.

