Aims 3 and 4 Test whether the intervention group has more appropriate health care utilization and lower total health care costs. We will analyze utilization for three separate outcomes: ED visits, outpatient visits, and inpatient hospital admissions as we would expect the intervention to result in declines in ED and inpatient care with concomitant increases in outpatient care over time as patients stabilize their health status. For these analyses we will use a rate modeling approach (negative binomial or Poisson regression, with an exposure adjustment should there be a need to account for differing amounts of follow-up time). We will examine health care costs (combined hospital and ambulance costs) from the health care system perspective.

Mean-per-month health care costs will be calculated for both pre- and post-randomization periods for each individual. We will assess the difference in health care costs across the two study arms by regressing post-randomization mean health care costs on study arm, and controlling for pre-randomization mean health care costs (which should reduce variance and increase power) along with other important covariates. We expect that 500 per arm will be an adequate number to support the use of Ordinary Least-Squares (OLS) regression to model mean cost differences, but will use Generalized Linear Models (GLM) models to examine the sensitivity of OLS results. In addition, we will calculate unadjusted and adjusted cost offsets by adding the cost of the intervention to health care costs and comparing average monthly total costs of services for the intervention group to the average for the standard care group.

Aim 5 Test whether the intervention group has fewer HIV risk behaviors. These are measured as both binary and continuous data. Binary data will be examined with logistic regression and continuous data analyzed with ordinary least-squares regression.

Other analyses

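### Aim 4 claims total health care costs, but the analysis counts only hospital and ambulance costs, so a reported saving could omit a rise in drug treatment or non-hospital outpatient care

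*Combined protocol and SAP*

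**What the plan says.** Under Objectives, Secondary Aims, the fourth aim is "Lower total health care costs". The Aims 3 and 4 paragraph of Planned analyses repeats the total-cost aim and then defines what is measured: "We will examine health care costs (combined hospital and ambulance costs) from the health care system perspective". The measures table (Schedule of and Sources Data Obtainment) labels the outcome "Hospital-based total direct health care costs". The cost-offset step adds one item, the cost of delivering the intervention, and then compares the arms on mean monthly totals.

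On use of services, the Aims 3 and 4 paragraph expects "declines in ED and inpatient care with concomitant increases in outpatient care over time as patients stabilize their health status". The BBCC section says that if subjects indicate in the session that "they would prefer to quit opiates or to seek opiate detox or treatment, the interventionist will help with these referrals". Secondary Data Sources lists the state TARGET system "for drug treatment admissions data". The measures table also lists opioid substitution and other drug treatment as interview items under Aim 2. None of these treatment data is given a cost anywhere in the plan.

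**The concern.** A total-cost result from the health care system perspective should include every service that the intervention can plausibly shift. Here the services expected to fall (emergency and inpatient care) are inside the cost outcome. Drug treatment, which the intervention may increase, is outside it, and so is outpatient care delivered away from hospitals. If patients move from costed to uncosted care, the fall is recorded and the rise is not.

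At stake is the interpretation of Aim 4 and of the cost offset. A reader would take a reported saving as a saving to the health care system, when part or all of it could be spending moved to providers whose costs were never counted.

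**Working it through.** The plan gives no cost, no expected cost difference and no power calculation for Aim 4, so there is no cost figure to reproduce. The 500 per arm quoted for the cost regression follows from Sample Size Calculation (250 per arm in each of two user groups, 250 + 250 = 500) and is not in question. The check is therefore a comparison of sections followed by an identity.

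**Step 1: what is costed, and which way the plan expects it to move**

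| Service | In the cost outcome? | Direction suggested by the plan |
|---|---|---|
| ED and inpatient care | Yes (hospital) | Down (Aims 3 and 4) |
| Ambulance | Yes | Not stated in Aims 3 and 4 |
| Outpatient care at hospital-run clinics | Not stated | Up (outpatient care generally) |
| Outpatient care outside hospitals | No | Up (outpatient care generally) |
| Drug treatment | No | May rise (opening summary on brief counselling; BBCC referrals) |
| The intervention itself | In the offset only | Intervention arm only |

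**Step 2: the identity.** Per subject-month, let

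- M = control mean minus intervention mean of hospital and ambulance cost (the measured saving);
- I = cost of the intervention;
- U = intervention mean minus control mean of uncosted care.

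The plan reports M as the cost difference and M − I as the offset. The all-service quantities are M − U and M − I − U. Both reported results are therefore too favourable by U when U is positive, and too unfavourable when U is negative.

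**Step 3: illustration in assumed units.** Take a control-arm hospital and ambulance cost of 100 units a month and a measured saving M = 20. Neither figure is in the documents.

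| U as a share of M | U | All-service saving, M − U | Saving the plan reports |
|---|---|---|---|
| 0% | 0 | 20 | 20 |
| 25% | 5 | 15 | 20 |
| 50% | 10 | 10 | 20 |
| 100% | 20 | 0 | 20 |
| 150% | 30 | −10 | 20 |

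The planned result is 20 in every row. The sign of the conclusion reverses once U exceeds M.

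**Step 4: does another planned analysis pick up U?**

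- Adjusting for pre-randomization cost reduces variance but adds no missing component.
- The GLM models test the form of the OLS model, not the content of the outcome.
- Outpatient visits are counted under Aim 3 and treatment is recorded under Aim 2, but neither enters the cost estimate.
- The completeness check under Other analyses records outside services in broad categories, without costs, and changes no estimate.

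**The case against.** The strongest reply is that the cost scope is stated openly, that this is a secondary aim, and that a shift in care would show up beside the cost result in the outpatient counts and the drug treatment measures. That is fair as far as it goes. It limits the risk of a misleading conclusion, but the label and the estimate stay as they are.

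Three stronger readings are tempting, and the documents do not support them.

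- *All outpatient care is left out.* A reader might infer this from the contrast between hospital costs and rising outpatient use. But hospital costs may include clinics run by the study hospitals, and nothing in the Aims 3 and 4 paragraph restricts them to emergency or inpatient care. The measures table is broken at exactly the row that lists outpatient use, so it cannot settle the matter. The omission is firm only for drug treatment and for outpatient care outside hospitals.
- *The omitted costs rise in the intervention arm by design.* Intervention Description says standard care may itself include referral to drug treatment or detoxification. The interventionist's help depends on the subject expressing a wish for treatment. Enrolment in opioid substitution is one of the listed elevated-risk criteria, so some subjects in both arms will already be in treatment, which limits the room for a difference. A positive U is plausible, not guaranteed.
- *The bias can be given in dollars.* The documents contain neither a treatment cost nor an expected difference in treatment entry, so any dollar figure would only restate its own assumptions.

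A further objection stands. Full costing is not a matter of using data already in hand. Secondary Data Sources describes the state data as awaiting separate IRB action and TARGET as admissions data, with no mention of duration or intensity. Interviews stop at 12 months, while administrative follow-up runs to at least 24.

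**Conclusion.** The concern holds in limited form. The aim and the offset are worded more broadly than the outcome that will be measured: drug treatment and non-hospital outpatient care carry no cost, and the handling of hospital-run outpatient care is unstated. The plan's own expectations make a bias toward savings possible, and its likely direction follows from them. Its size equals the between-arm difference in uncosted care, which the documents do not allow anyone to compute.

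The conclusion about direction assumes that the intervention raises treatment entry or non-hospital outpatient use more than standard care does. The mismatch between label and outcome needs no such assumption. The overdose outcome and its sample size are unaffected.

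**What to change.** 1. In Objectives (Secondary Aims) and in the Aims 3 and 4 paragraph, restate the outcome and the cost offset as *hospital and ambulance costs*. Drop the claims to total cost and to a full health care system perspective. Align the hypothesis in the opening summary and the label in the measures table.
2. State whether hospital-based outpatient care is part of the hospital cost.
3. If the TARGET data are obtained, add a sensitivity analysis that values drug treatment at standard unit costs over a stated range and adds it to both the cost difference and the offset. Specify how visits already billed by a hospital will be excluded, so that nothing is counted twice.

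The first two changes need no new data; their cost is a narrower claim. The third depends on access to the state data and gives only an approximate figure, because unit costs would be applied to admissions. That is why it belongs in a sensitivity analysis and not in the main cost outcome.

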- 2) Overdose Risk Assessment: This assessment is used to determine the potential for future overdose based on prior overdose history, current drug use practices and social context for current drug use. This assessment is not standardized but is compiled from individual items of known risk factors for overdose.
- 3) World Health Organization Quality of Life (WHOQOL-BREF). This is a short assessment to measure general health and physical, social and emotional functioning.
- 4) World Health Organization Alcohol, Smoking and Substance Involvement Screening Test (WHO-ASSIST v.3). This is a multi-item tool to determine areas of substance use and misuse. This assessment battery screens for recent and lifetime use of a variety of substances, including illicit drugs, alcohol, pharmaceuticals and tobacco products.
- 5) Age of First Use: Subjects are asked to provide the ages they first used a variety of substances.
- 6) HIV Risk Assessment Battery: This assessment is used to determine the potential for contracting HIV, hepatitis and other blood-borne illnesses based on drug use and sexual use behaviors.
- 7) Overdose History: This assessment will collect information related to any prior overdose that the subject has experienced or witnessed.
- 8) EQ-5D-3L: This validated quality of life measure asks about problems in mobility, self-care, usual activities, pain and discomfort, anxiety and depression and overall health.

Locator information:

Subjects will be asked to provide a number of sources to ensure they can be contacted for 3, 6 and 12 month follow-up visits. However, because we anticipate a number of high risk subjects to be indigent, subjects may be enrolled if they provide at least one primary source of locator information.

Randomization

Subjects will be randomized to receive either standard of care or the study intervention. We will recruit equal numbers of subjects in the intervention and control arms of the study, meeting eligibility criteria as heroin user or primarily pharmaceutical opioid users.

Follow-up Visits

Follow-up visits will occur at 3, 6 and 12-month after enrollment. All interviews will be by phone. Most assessments given at the baseline interview will be repeated at each follow-up

point. In addition to the assessments subjects will be asked questions about whether they have naloxone and, if not, what happened to any naloxone that was given to them.

Secondary Data Sources

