Aim 1 Test whether the intervention group has lower rates of opioid overdose and longer time to occurrence of overdose. Overdose will be ascertained at 12 months via self-report and across at least 24 months via administrative data. Because randomized controlled studies are designed to account for potential confounding factors by distributing confounders, measured and unmeasured, equally across comparison and intervention groups, the initial unadjusted analysis will be a logistic regression analysis comparing the probability of opioid overdose in the two study arms. To examine differences in the time to overdose and to account for time varying covariates, such as overdose risk factors, survival analyses will be conducted with the outcome time to overdose(s). A Cox proportional hazards model will be used to investigate the possible association between these factors and event time. We will use sandwich standard error estimates in all statistical tests. Multivariable logistic regression analyses will be conducted to examine the association between predictors and moderators and of the odds of overdose occurrence. Predictors will include treatment assignment and overdose risk factors such as concomitant drug use, interruption in tolerance and homelessness. Potential effect modification will be assessed by including interaction terms for the treatment assignment by severity of opioid and other substance use as measured by the ASSIST. For the pharmaceutical opioid only group, effect modification by opioid user type will be assessed; opioid user typologies will be based upon which inclusion criteria subjects met.

Aim 2 Test whether the intervention group has fewer overdose risk behaviors. These are measured as both binary and continuous data. Binary data will be examined with logistic

regression and continuous data analyzed with ordinary least-squares regression. Analyses will adjust for the overdose risk behavior level or frequency reported at baseline as a concomitant variable, the outcome is the overdose risk behavior at 12 months, and the primary predictor is the treatment group assignment. We will compute robust standard error estimates for each model and use them in all hypothesis tests and confidence intervals.

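### Aim 5 omits the baseline adjustment that Aim 2 makes with the same models, so it gives up precision in a secondary aim; Aim 3 could gain likewise, but only where prior visit counts exist

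*Combined protocol and SAP*

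**What the plan says.** All models are in Data Analysis, Planned analyses.

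- **Aim 5:** "Aim 5 Test whether the intervention group has fewer HIV risk behaviors. These are measured as both binary and continuous data". The only other sentence assigns logistic regression to binary measures and ordinary least squares to continuous ones. No covariate and no outcome time point is named.
- **Aim 2:** the same two models, with the addition "Analyses will adjust for the overdose risk behavior level or frequency reported at baseline as a concomitant variable". The outcome is set at 12 months.
- **Aim 3:** "We will analyze utilization for three separate outcomes: ED visits, outpatient visits, and inpatient hospital admissions". The model is "negative binomial or Poisson regression, with an exposure adjustment should there be a need to account for differing amounts of follow-up time". Exposure time is the only adjustment mentioned.
- **Aim 4,** under the same heading as Aim 3: "Mean-per-month health care costs will be calculated for both pre- and post-randomization periods for each individual". Post-randomization cost is then regressed on arm, "controlling for pre-randomization mean health care costs (which should reduce variance and increase power". The scope is narrow: "We will examine health care costs (combined hospital and ambulance costs) from the health care system perspective".

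Baseline Assessments lists the "HIV Risk Assessment Battery: This assessment is used to determine the potential for contracting HIV, hepatitis and other blood-borne illnesses". Follow-up Visits says that most baseline instruments are given again at each contact, and the schedule table has an Aim 5 row. Objectives places Aims 3 and 5 among the secondary aims, and the opening summary presents the HIV question as exploratory.

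**The concern.** The plan gives an efficiency reason for controlling for the pre-randomization level in Aim 4 and makes the same kind of adjustment in Aim 2. It gives no reason for leaving Aims 3 and 5 without one. For Aim 5 the covariate is already being collected. What is at stake is the width of the confidence intervals and the power in these secondary aims.

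A second issue is specification. With no covariate named, adjusted and unadjusted results are both defensible once the data are in. For binary measures the two odds ratios estimate different quantities.

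**Working it through.** **The plan's own figure.** Neither aim has a stated power or sample size. The only such figure is 219 per arm for Aim 1 (Sample Size Calculation: 20% versus 10%, power 0.80, level 0.05). A two-sided calculation gives n' = [1.95996·√(2·0.15·0.85) + 0.84162·√(0.20·0.80 + 0.10·0.90)]² / 0.10² = 198.96. With the continuity correction, n = (n'/4)·[1 + √(1 + 4/(n'·0.10))]² = 218.5, hence 219. The figure reproduces, and no baseline correlation enters it.

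**Is the covariate supplied elsewhere?** Aim 4's catch-all mention of further covariates sits inside the cost model. The covariate block of the schedule table is tied to no aim and lists neither baseline HIV risk nor prior visits. So it is not.

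**Aim 5, continuous measures.** The baseline correlation ρ is assumed. The variance factor is 1 − ρ². For an effect with power 0.80 unadjusted (1.960 + 0.842 = 2.802), adjusted power is Φ(2.802/√(1 − ρ²) − 1.960). The detectable effect is 2.802·√(2(1 − ρ²)/n) SD; unadjusted it is 0.177 SD at 500 per arm and 0.251 SD at 250.

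| ρ | Variance cut | Power | Detectable, 500/arm | Detectable, 250/arm |
|---|---|---|---|---|
| 0.1 | 1% | 0.80 | 0.176 | 0.249 |
| 0.3 | 9% | 0.84 | 0.169 | 0.239 |
| 0.5 | 25% | 0.90 | 0.153 | 0.217 |
| 0.7 | 49% | 0.975 | 0.127 | 0.179 |

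**Aim 5, binary measures.** Assumed: marginal risks 40% versus 30%, baseline prevalence 40%, logistic model with robust SE, 4,000 simulated trials per setting. The marginal odds ratio is (0.30/0.70)/(0.40/0.60) = 0.64. Unadjusted power is about 0.91–0.92 at 500 per arm and 0.66 at 250. The unadjusted log-odds SE at 500 per arm is 0.134.

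| Baseline phi | Conditional OR | Adjusted SE, 500/arm | Power, 500/arm | Power, 250/arm |
|---|---|---|---|---|
| 0.1 | 0.64 | – | 0.92 | 0.66 |
| 0.3 | 0.62 | 0.140 | 0.93 | 0.69 |
| 0.5 | 0.56 | 0.155 | 0.97 | 0.77 |
| 0.7 | 0.44 | 0.189 | 0.996 | 0.90 |

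Power rises although the SE rises, because the conditional odds ratio lies further from 1.

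**When is the unadjusted estimate unbiased?** A simulation used a continuous outcome, ρ = 0.5, true effect −0.20, 500 per arm and 1,500 runs. With complete follow-up the unadjusted mean was −0.201 (SE 0.063) and the adjusted mean −0.201 (SE 0.053). The log-odds of retention were then set to 1.4 in the control arm and 1.4 − 0.8 × baseline in the intervention arm. The unadjusted mean became −0.283; the adjusted mean stayed at −0.201. This dropout pattern is an assumption, not a forecast.

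**Aim 3.** Assumed: rate ratio 0.8, frailty variance 1, 500 per arm, gamma-frailty Poisson counts, Poisson model with robust SE, covariate log(prior count + 1), 6,000 trials per setting. Unadjusted, by formula:

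- Control mean 2: variance [(1/2 + 1) + (1/1.6 + 1)]/500 = 0.00625; z = 0.2231/0.0791 = 2.82; power 0.81.
- Control mean 0.5: variance [(1/0.5 + 1) + (1/0.4 + 1)]/500 = 0.0130; z = 0.2231/0.1140 = 1.96; power 0.50.

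The pre/post correlation cannot exceed mean × variance/(1 + mean × variance), which is 2/3 = 0.67 for mean 2 and 0.5/1.5 = 0.33 for mean 0.5.

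| Control mean | Pre/post correlation | Variance cut | Simulated power, unadjusted to adjusted |
|---|---|---|---|
| 2 | 0.17 | 2.5% | 0.80 to 0.82 |
| 2 | 0.33 | 10% | 0.81 to 0.85 |
| 2 | 0.50 | 24% | 0.81 to 0.90 |
| 0.5 | 0.08 | 0.6% | 0.51 to 0.51 |
| 0.5 | 0.17 | 2.5% | 0.50 to 0.51 |
| 0.5 | 0.25 | 5.7% | 0.51 to 0.53 |

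At rate ratio 1 (mean 2), rejection rates were 0.053 and 0.048 unadjusted and 0.050 and 0.052 adjusted, so both tests hold their level. At 250 per arm and mean 2, z = 2.82/√2 = 1.99 gives power 0.51. Dividing by √0.763 (the 24% cut, unrounded) gives 2.28 and power about 0.63.

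Many subjects are found through an ED or inpatient visit (Potential Subjects Identified). Requiring at least one prior visit in the same model lowered the variance cut from about 11% to 9% and from about 25% to 21% at mean 2, and from about 6% to 4% at mean 0.5.

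**The case against.** The strongest reply is that nothing here is an error. Unadjusted comparisons are valid under randomization, baseline adjustment is optional, and both aims are secondary. That stands, and it caps the severity.

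A second reply is that silence is not exclusion. Aim 1 labels its first analysis unadjusted; Aims 3 and 5 name regression models without that label. This also stands in part: the text leaves covariates unspecified and does not rule them out. But an analyst who follows the text has no baseline term to include, and the contrast with Aims 2 and 4 remains.

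A third reply concerns Aim 3. The plan describes pre-randomization data only as costs, limited to hospital and ambulance. Secondary Data Sources cites the state hospital system for admissions, and Other analyses treats the hospital and ambulance records as possibly incomplete. A reader might infer that prior counts of all three visit types are already in hand; the documents do not show this. The Aim 3 part is therefore conditional.

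Finally, every input to the size estimates is assumed. They show what could be gained, not a demonstrated loss.

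**Conclusion.** The point holds for Aim 5: the plan repeats Aim 2's models without the baseline term, the covariate is collected, and the analysis as written is valid but less precise than it could be. The gain runs from negligible at a correlation of 0.1 to about half the variance at 0.7; the documents do not narrow that range. For Aim 3 the point is secondary and conditional on available counts. There the gain is small for rare visit types and somewhat lower than tabulated for subjects recruited through an ED or inpatient visit.

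Two stronger readings should be resisted. One is that the omission makes Aims 3 or 5 invalid or inflates type I error; randomization and the simulated rejection rates argue against that. The other is that the unadjusted Aim 5 estimate is free of bias without condition. That requires loss to follow-up not to depend on baseline risk differently by arm. Missing data and dropouts concedes possible bias, and its only specified sensitivity analysis carries forward drug use, not HIV risk behavior. The documents do not show that such differential loss will occur.

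Severity is minor: secondary aims, and no stated figure changes.

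**What to change.** **Aim 5.** Add: *Analyses will adjust for the baseline value of the same HIV risk measure.* State the outcome time point, as Aim 2 does. For binary measures, say that the adjusted odds ratio is conditional on baseline, or also report a standardized risk difference. This costs a few sentences of analysis-plan text and no new data. The one drawback is that the conditional odds ratio has a larger log-scale SE and is not comparable with an unadjusted one, so the estimand must be written down.

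**Aim 3, conditional.** Where the records obtained for Aim 4 give pre-randomization counts of the same visit type (ED, inpatient or outpatient), include that count, for example as log(count + 1). State the look-back window and whether the recruiting visit is counted. Where they do not, say that the model for that visit type is unadjusted. The cost is an extraction of prior counts by type, whose effort depends on what the records hold. No additional subjects or visits are needed.
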